A9. ClinicalTrials.gov Registration

Does this protocol/trial require registration on ClinicalTrials.gov due to it: meeting the definition of an Applicable Clinical Trial, being required under the terms and conditions of an award, or being proposed to be published in ICMJE journals?

Yes

Who will be responsible for registering and maintaining the registration of this Applicable Clinical Trial?

The BCM PI will register the trial because either:

- the trial is BCM PI-initiated,
- BCM is the lead site of this multicenter trial, or,
- the industry sponsor has instructed the BCM PI to register the trial, or,

- registration of this trial is required as a term and condition of the reward by the funding agency.

ClinicalTrials.gov Identifier:

NCT04807387

Section B: Exempt Request

B. Exempt From IRB Review

Not Applicable

Section C: Background Information

There is an Urgent Need for a Commercially-Available Vaginal Stents. As many as 50,000 patients per year in North America require the surgical reconstruction of a new vaginal canal [1]. The success of this procedure is dependent how well the vaginal tissues are kept from apposing one another during the post-surgical period [1]. Currently, there are no effective methods to maintain the separation of vaginal tissues vaginal reconstruction. A vaginal stent is a medical device with an inner rigid core surrounded by an inflatable balloon that is placed into the vaginal canal postoperatively such that the vaginal walls do not appose each other during the healing process. The importance of efficacious vaginal stents in the success of neo-vaginal creation in post-adolescent populations cannot be overstated; if the new vaginal canal does not maintain its patency while the tissues heal, postoperative complications may occur. The most common complication after vaginal reconstruction is restenosis and scar tissue formation, which can occur in up to 73% of patients, necessitating persistent perineal dilatation using vaginal dilators after surgery in order to maintain the caliber of the neo-vagina [2] in order to maintain the ideal vaginal structure (such as ideal length) and to avoid expensive and unpleasant surgical revisions.

For adult women undergoing surgery or gynecologic cancer treatments, the effects on vaginal length and quality of life are significant. About 19% of women after hysterectomy alone experience substantial vaginal length reduction and more than 100,000 women per year in the United States seek treatment for vaginal foreshortening causing dyspareunia [3,6]. After pelvic surgery and/or pelvic radiation for treatment of gynecologic cancers, up to 88% of women will develop significant vaginal stenosis with shortening, scarring with narrowing of the vagina leading to dyspareunia, tissue friability, and vaginal bleeding and pain [4,5]. Sexual dysfunction can be as high as 33% in women undergoing radiation therapy and quality of life for these women can be compromised [6]. Significant vaginal scarring may occur in 1/70 women due to dermatological diseases such as lichen sclerosis [10]. The only method to maintain the vaginal caliber postradiation is with the use of vaginal dilators after radiation treatments have concluded. Despite the vital role perineal dilation plays in restoring normal vaginal function, and in maintaining quality of life, adherence to the recommended dilation regimes is consistently low, with less than 50% of females using dilators at the recommended frequency, and as many as 75% stopping the use of the dilator within a year [11]. A vaginal stent placed after radiation treatments may maintain the vaginal caliber, reduce post-radiation fibrosis, and eliminate the need for perineal dilatation. Thus the role of vaginal stents for successful outcomes after neovaginal surgery and post-radiation is even more clear.

Post-operative difficulties with healing are even more problematic in the pediatric population, due to the simple fact that no commercially-available vaginal stent has ever existed for adolescents to prevent the need for difficult and unpleasant dilation regimes which show low patient adherence. Recent increases in malformations such as specific congenital genitourinary anomalies [12], and a societal shift towards better acceptance of male-to-female transgender surgeries have led to a surge in the number of surgeries for neo-vaginal creation in girls and young women. There are as many as 50,000 girls per year and 213,000 women per year who could benefit from postoperative treatment using newly designed vaginal stents [1,3]. Extensive scar tissue formation in the vagina, vaginal restenosis and vaginal foreshortening can have profound effects on young girls and women. As in the post-radiation population, the need for persistent dilatation post-surgery can lead to early discontinuation due to noncompliance or to significant complications including vaginal bleeding or even perforation of the vagina or bladder and fistula formation [4]. Many pediatric surgical centers quote a risk of surgical revision after vaginal reconstruction to be about 50% [5].

The availability of a vaginal stent for the pediatric and post-radiation populations offers unimaginable benefits: by reducing the need for perineal dilation, vaginal stents offer the promise of a reduction in vaginal scar tissue formation, in post-surgical and post-radiation morbidity, surgical revisions, lifelong perineal dilatation, and improvement in sexual function. Together, the improvements to the quality of life of these populations would yield physical and psychological benefits for both patients and families as well as significant health care cost savings.

Current Vaginal Stents are hand-crafted and outcomes are poor. In adolescent populations, hand-crafted, ill-fitting

vaginal stents are routinely placed via a number of procedures which can vary enormously by indication. Some inpatient procedures require stays in hospital with a tractioned vaginal stent for up to 5 days. These patients then wear a stent intermittently thereafter for up to 4 weeks depending on vaginal healing. Outpatient procedures may require use of a vaginal stent intermittently for up to two weeks. Patients are currently required to be able to remove and reinsert the vaginal stent themselves at home (usually same stent that is washed and re-used). However, due to the relative non-existence of a commercially available product, physicians are relegated to creating their own makeshift stents for their gynecology patients either using finger slots from sterile gloves and gauze, sterile cement coated in bone wax and placed in a condom, or plastic moulding. All of these are suboptimal options with resultant low patient compliance, stent egress and emergency room hospital visits for replacements, and poor patient outcomes.

Adult vaginal stents used to exist (Mentor Stent, Coloplast, Inc.), and were sold up until 2010 by Coloplast, when despite enormous benefits to patients, these devices were withdrawn due to financial and legal issues surrounding an entirely different device made by the same company. Coloplast had previously acquired Mentor's urogynecologic line that included vaginal stents, and discontinued the product after massive recalls on their breast implants due to safety issues and it was never replaced. A new company PMT corporation has recently begun selling the previous Mentor Stents with no design changes. Both the Mentor stent and makeshift devices frequently fall out, and are associated with a high numbers of complaints regarding their discomfort. Many patients require their labia sutured around the stent in order to retain it. Despite being one of the only ways to prevent the need for perineal dilation and subsequent surgical revision, difficulties with these devices lead to low patient compliance. More concerning, there has never been a vaginal stent designed for, and tested on a pediatric population. This population is left vulnerable to effects of being forced to rely on procedures such as perineal dilation for good outcomes. The need to help these patients and their physicians with a simple device that can improve both surgical outcomes and patient quality of life beyond surgery cannot be overstated. Similarly, the commercial potential for this project to lead to marketable product is significant as there is pent up demand for this product. This along with the larger commercial markets outlined in the commercialization plan, and the experience of this team in bringing novel products to market, greatly increase the chances for commercial success.

A Predicate Device for Stents in Pediatrics. We have assembled a unique team of engineers, commercialization experts, and clinicians, representing the first group, to our knowledge, to design a vaginal stent system that addresses the anatomic needs of the pediatric patients, and could be expanded to use in a much larger post-gynecologic cancer patient population. Members of our team, as well as those of our outside advisory board of pediatric gynecology and gynecologic oncology experts have strong confidence in the potential of our device to eliminate post-surgical stricture, facilitate physician procedures, and reduce early discontinuation in patients. Our work supporting this premise will be presented at the 2021 North American Society for Pediatric Adolescent Gynecology (NASPAG) Annual Clinical Meeting, and published in their conference literature. Our group, at this time, is on the cusp of improving outcomes for tens of thousands of girls every year undergoing vaginal surgery and those women undergoing radiation treatments. Now is the time to move this project forward and optimize the stent design and complete steps required for commercialization so it can reach patient populations as soon as possible, reducing the need for dilation and / or surgical revision in females who have undergone neovaginal surgery or radiation treatments.

(Works cited and copy of NIH grant submission are attached in Section S.)

Section D: Purpose and Objectives

This proposal seeks to develop a production-ready novel vaginal stent specifically designed to improve postsurgical outcomes with regard to restenosis for girls who have undergone neo-vaginal creation and for women who have undergone pelvic surgery or radiation due to gynecologic cancer treatment. In our Phase I project we designed, built, and tested multiple configurations of our stent design, performed bench-top testing in anatomical models and excised porcine tissue using our stent prototypes, and evaluated the performance of the vaginal stent prototypes *in vivo* in a porcine animal model. In this Phase II project, we will refine the current device into a final clinically-ready format, test usability factors in a population of healthy volunteers, and finally evaluate its use in a broad cohort of our target clinical populations. The end result of this effort will be a new clinical instrument specifically designed for maintenance of the vaginal caliber after surgery and/or pelvic radiation.

Specific Aim I: Finalize design for a clinical-ready version of our vaginal stent system and perform preliminary verification and validation testing.

1a: Optimize the stent design. Biotex engineers will integrate our current prototype designs into two different inflatable configurations which cover desired diameters and length ranges. Efficacy of our vaginal stent is shown by its retention in the vaginal canal for 2 weeks. We will work closely with clinical collaborators to refine our stent designs as well as insertion and retrieval tools with the goal to finalize stent materials, size ranges, and factors which will improve patient compliance with stent use.

1b: Completion of product testing required for FDA submission and commercialization. Vital steps towards enabling product distribution include performing required validation activities (biocompatibility, sterilization, packaging,

performance testing) for FDA 510(k) submission. After finalization of stent designs, product development engineers will develop protocols under design controls, manage production of final units, and execute required testing.

Specific Aim II: Examine the acceptance and success of our novel vaginal stent in healthy (non-clinical) subjects. Accruing clinical samples large enough for both development and testing can be prohibitive due to the low numbers of adolescent patients at any one institution requiring neovaginal surgery. In addition, clinical samples can be heterogeneous on key variables which may relate to the success of our stent, such as age, maturity, or comorbid conditions. Therefore, we will conduct aim 2 in a non-clinical population.

2: Quantify key factors to better understand stent efficacy. In 20 non-clinical volunteers, we will associate factors such as design, pull-out forces, comfort, and inflation/ deflation / retrieval ergonomics with stent retention.

Specific Aim III: Evaluate the success of our vaginal stent in a broad cohort of clinical subjects. After establishing the regulatory (aim 1), practical (aims 1 and 2) and patient factors (aim 2), we will use this information to inform the protocol of our pseudo-clinical trial in aim 3.

3a: Demonstrate vaginal stent retention in the vaginal canal for two weeks in a clinical population. In 10 post-surgical patients and 10 post-radiation adult women, the efficacy of our novel vaginal stent will be demonstrated both through lack of egress and through patient compliance to using the device.

3b: Demonstrate that retention of our novel vaginal stent in the vaginal canal is superior to that of existing makeshift / handmade vaginal stents.

By leveraging the unique medical database available at our institutions (Texas Children's Hospital and Baylor College of Medicine), we will demonstrate success of our new vaginal stent by comparing the number of vaginal stents still in place at a 2-week post-surgical follow-up in neovaginal surgery.

Section E: Protocol Risks/Subjects

E1. Risk Category

Category 2: Research involving greater than minimal risk, but presenting the prospect of direct benefit to the individual subjects.

E2. Subjects

Gender:

Female

Age:

Adolescent (13-17 yrs), Adult (18-64 yrs)

Ethnicity:

All Ethnicities

Primary Language:

English, Spanish

Groups to be recruited will include:

Both patients and healthy, non-patient, normals

Which if any of the following vulnerable populations will be recruited as subjects?

Children

Vulnerable populations require special protections. How will you obtain informed consent, protect subject confidentiality, and prevent undue coercion?

Informed consent will be obtained by trained research personnel. An initial screening interview via phone will be held, followed by an invitation to speak with a study coordinator (plus interpreter if needed). The study risks and procedures will be fully explained, eligibility assessed, and the participants' rights enumerated (including the right to withdraw at any time). Potential participants will be given time to answer questions. For subjects under age 18, parental consent and adolescent assent will be obtained prior to participation. Subject confidentiality will be maintained at all times; phone calls and in-person recruitment will be held in private rooms. All patient information will be kept on a secure, HIPAA-compliant electronic server or in a locked file cabinet when not in use.

Please note The Spanish forms -consent form, recruitment flyers, questionnaires- are being translated as of 2/2/21.

We will attach these forms when translation is complete.

E3. Pregnant woman/fetus

Will pregnant women and/or fetuses (as described in 45 CFR 46 Subpart B) be enrolled in the research?

No

E4. Neonates

Will neonates of uncertain viability or nonviable neonates (as described in 45 CFR 46 Subpart B) be enrolled in the research?

No

E5. Children

Will children be enrolled in the research?

Yes

Section F: Design/Procedure

F1. Design

Select one category that most adequately describes your research:

K) Device, Phase II, Single Center

Discuss the research design including but not limited to such issues as: probability of group assignment, potential for subject to be randomized to placebo group, use of control subjects, etc.

This is a non-randomized clinical trial of healthy and patient cohorts, females ages 13-64 years will be recruited into different groups. 20 healthy participants (ages between 13-64 years) will be recruited initially to try wearing 2 stents separately for 24 hours each, provide feedback, then wear the preferred stent for 2 weeks. Subsequently, 20 patient participants, 10 post-surgical adolescent patients and 10 post-radiation adult patients, will be recruited to wear the stent for 2 or 4 weeks, respectively. Neither healthy nor patient participant will be randomized. (Procedure details in section F2.) A control cohort will not be recruited; rather, within-group outcomes will be measured. The adolescent versus adult female patient outcomes will also be compared.

Physician participants will be asked to complete a post-stent questionnaire which will evaluate the level of difficulty with stent insertion and removal.

Inclusion Criteria:

Healthy volunteers: (a) female between 13-64 years of age, (b) not currently pregnant, (c) if under age 18, parents must be able to give informed consent and volunteer must give informed assent, (d) ability to understand the requirements of the study and abide by the restrictions, (e) ability to travel to Houston for study evaluations, (f) ability to understand English or Spanish to a grade 5 level, (g) no history of prior vaginal surgery or radiation.

Patient volunteers: (a) adolescent female patients, ages 13-18 undergoing vaginal reconstructive surgery at high risk for vaginal fibrosis including those with transverse vaginal septa, vaginal atresia, or post-radiation, (b) adult female patients undergoing vaginal brachytherapy for cancer at high risk of vaginal fibrosis, (c) not currently pregnant, (d) ability to give informed consent (If patient is under age 18, must be able to give informed assent with parent consent), (e) ability to understand the requirements of the study and abide by the restrictions, (f) ability to travel to Houston for study evaluations, (g) ability to understand English or Spanish to a grade 5 level.

Physician volunteers: Physicians who oversee the patient volunteers and deploy the current vaginal stent post surgery/post radiation will be asked to complete a Physician Post-Stent Questionnaire (attached to Section S).

Exclusion Criteria:

All volunteers: (a) Non-English or Spanish language (b) pregnant patients (c) women with BMI >45 (d) women with prior vaginal surgeries (e) women with comorbid conditions such as diabetic neuropathy or other conditions limiting use of hands for stent removal, vaginismus, urinary retention, bacterial or fungal infections, allergies to stent material such as silicone, seizure disorder. (f) in healthy participants only: any pain with sexual intercourse or tampon insertion. in post-surgical and post-radiation participants: pain >5 on a 10 pt Likert Scale with sexual intercourse or tampon insertion

F2. Procedure

This study has 3 phases. Phase 1: 20 healthy volunteers to determine the better of 2 stents, based on highest retention and comfort. Phase 2: the same 20 healthy volunteers will wear the stent for 2 weeks to evaluate retention and comfort. Phase 3: 20 patient volunteers (adolescent females after surgery and adult females after radiation treatment) will evaluate stent on same criteria. During all phases, the option of obtaining vaginal pressure measurements will be available. For pressure measurements, a pressure gauge will be attached to the end of the stent, outside of the vagina, and the pressure between the stent and vagina will be measured as the participant lies, stands, squats, walks around the clinical room, and intentionally exerts downward pressure in the vaginal cavity. The pressure will be measured for 1 minute during each activity, after which the pressure gauge will be removed.

Phase 1: 20 Healthy volunteers will be recruited through flyers placed at hospitals, research institutions, and device accelerators within TMC, the study recruitment pages of BCM website, and through the electronic BCM and TCH newsletters. Social media will be used to promote the study with a direct link to the BCM recruitment page. All comments and replies will be disable and no PHI will be obtained or discussed via social media. (See Section S). Following an initial screening call with research personnel, eligible participants will be invited to TCH for orientation and to obtain consent by a study coordinator (interpreter if needed). Participants will then undergo a urine pregnancy test, vaginal assessment via visual exam, speculum, or colposcopy to assess vaginal mucosa and a vaginal swab to rule out presence of bacterial or fungal infections. Physicians will complete the Vaginal Assessment Form (VAF). Participants will complete a Pre-Stent Questionnaire to establish any vaginal baselines that may effect stent performance and a trained clinician will insert one of two stents. Instructions will be reiterated to the participant. After 24 hours, the participant will return to the clinic and the clinician will remove the stent. A vaginal exam and culture will be performed to ensure the tissue is intact and the participant did not experience any unexpected adverse events (AE). The participant will complete a Phase I Questionnaire and the clinician will complete VAF. The participant will return 24 hours later for a vaginal exam and culture, the clinician will insert the second stent, and the patient instructions will be reiterated. The participant will wear the second stent for 24 hours, return to clinic for removal, exam, and culture and both clinician and participant will complete the same questionnaires.

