a) Post-Surgical Adolescent Patients: Subjects will complete Pre-Stent Questionnaire. Prior to surgery, patients will undergo standard of care (SOC) testing including urine pregnancy and infection screening. The vaginal canal and mucosa will be assessed while in the operating room by vaginoscopy and a vaginal culture collected to rule out preoperative infection and vaginal length measurement. Vaginal surgery will be carried out per indication. A sterilized, vaginal stent will be placed postoperatively in the operating room, and instructions given to patients prior to discharge. Patients will continue to wear the vaginal stent for two weeks without removal and complete daily questionnaire on retention and comfort.

At 2 weeks post-surgery, patients will complete evaluation of the stent including tolerability, ease of use, comfort, reasons for early discontinuation, as well as any vaginal symptoms such as pain, bleeding or other AE. They will then be reassessed in the operating room (SOC) for stent removal, vaginal length measurement, vaginal culture, urinalysis, evaluation of the vaginal mucosa via vaginoscopy to assess for adhesions, granulation tissue, stricture, and remaining septal tissue. Physicians will complete the VAF.

Subsequent Visits: Patient participants will be re-evaluated at 4 and 6 weeks and 3, 6, and 12 months postop in the clinic. This visit frequency is considered SOC for adolescents who are postop from vaginal reconstructive surgery. Measured outcomes will include possible pain, bleeding, painful intercourse at 3 months postop, difficulty with tampon insertion, menstrual fluid retention, need for vaginal dilators. A physical exam will also be completed including a single digit vaginal exam to evaluate stricture, granulation tissue and adhesions. Patients may also be asked to demonstrate

placement of the vaginal stent (used as a corollary to adequate and maintained vaginal caliber).

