Participant feedback - Participants will be given questionnaires, via RedCap, with questions related to baseline vaginal metrics, stent comfort (during insertion, wear, removal), retention, ability to carry out normal Activities of Daily Living, and any AEs. At all points of instruction during clinic visits, patients will be given ample time to ask questions and voice concerns. A research coordinator or clinician will be available via phone for patient questions.

Section G: Sample Size/Data Analysis

G1. Sample Size

How many subjects (or specimens, or charts) will be used in this study?

Local: 40 Worldwide: 40

Please indicate why you chose the sample size proposed:

As a feasibility study, the low recruitment numbers will be used to evaluate the design concept with respect to functionality, comfort and any unforeseen safety issues (beyond those which were accounted for in earlier stages of the product design). The current participants will guide additional device refinements.

G2. Data Analysis

Provide a description of your plan for data analysis. State the types of comparisons you plan (e.g. comparison of means, comparison of proportions, regressions, analysis of variance). Which is the PRIMARY comparison/analysis? How will the analyses proposed relate to the primary purposes of your study?

Exploratory analyses of 20 healthy community participants: We code the stent as successful if, after 2 weeks, it has been retained in the vaginal canal. We will tentatively explore predictors of success using binomial logistic regression models, with a log-link estimator, which specify success (retained / not retained) as the outcome and participant group (under 18/over 18), and presence of bacterial / fungal infection at baseline and followup as three separate models. We will also run exploratory binomial logistic regression models, as above, with comfort, acceptability, ability to carry out normal Activities of Daily Living (ADLs), and number of AEs as outcomes, and participant group as the predictor. To maximize power, and recognize the exploratory nature of these analyses, we will not correct for multiple testing.

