Analyses of 20 clinical patient participants: Initial analyses will compare the two patient groups on baseline characteristics (vaginal cavity assessments by physicians and patient and physician questionnaires) using two sample t-tests, specifying patient group as the predictor. T-tests were selected for the robust to non-normal distributions with small sample sizes, and their suitability to small sample sizes as low as four per group (ref: york.ac.uk/depts/math/histstat/student.pdf). Our main analyses will examine whether the stent was successful in our population (ie. examining whether the proportion of retained stents was significantly different from zero). A one-sample t-test will be run, with success (returned at 2 weeks coded as 1, not retained coded as 0) as the independent variable. Significance will be set at $P < .05$.

All analyses will be conducted in the latest version of R (version 5.1.2).

Section H: Potential Risks/Discomforts

H1. Potential Risks/Discomforts

Describe and assess any potential risks/discomforts; (physical, psychological, social, legal, or other) and assess the likelihood and seriousness of such risks:

The participant may experience mild discomfort while using the stent. A thorough vaginal assessment will be performed by a clinician immediately after insertion to assess for any discomfort outside of normal range.

The likelihood of adverse events is small but could include bleeding, displacement of the stent such as egress, urinary retention, mucosal irritation, tearing, erosion, abscess, granulation tissue, or infection. The principal investigator will likely stop the trial for persistent displacement (>5), tearing or erosion of tissue, or abscess. The principal investigator will likely pause the trial and assess for further detail in instances of urinary retention, mucosal irritation, granulation tissue, or infection.

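### Aim 3b promises superior retention over handmade stents, but the visible plan specifies no such comparison, and the main test in G2, against zero retention, cannot show success

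*Combined protocol and SAP*

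**What the plan says.** **The aim.** Section D, Specific Aim 3b, undertakes to demonstrate that "retention of our novel vaginal stent in the vaginal canal is superior to that of existing makeshift / handmade vaginal stents". Its second sentence says this will be done from the medical database at the two institutions, by "comparing the number of vaginal stents still in place at a 2-week post-surgical follow-up in neovaginal surgery".

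**The design and procedures.** F1 says that no control cohort will be recruited and that outcomes are measured within groups. The one between-group comparison it names is adolescent against adult patients. F2 describes three prospective phases and no chart abstraction.

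**The numbers.** G1 asks how many subjects, specimens or charts will be used and answers "Local: 40 Worldwide: 40". It justifies this as a feasibility study. Aim 3a and F1 give 10 post-surgical and 10 post-radiation patients. F2, Phase 3, announces 20 patients and then lists 20 adolescents plus 10 adults.

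**The analysis.** For patients, G2 plans baseline t-tests between the two groups. Its main analysis is a one-sample t-test on retention at 2 weeks coded 0/1, "examining whether the proportion of retained stents was significantly different from zero", at P < .05 with no sidedness stated. Nothing in G2 compares the new stent with handmade stents.

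**Background on handmade stents.** Section C gives no retention rate. It says only that "Both the Mentor stent and makeshift devices frequently fall out".

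**Possible further detail.** Section C also notes that "Works cited and copy of NIH grant submission are attached in Section S". That attachment was not available for this review.

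**The concern.** There are two linked problems.

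First, a superiority aim against historical stents needs rules fixed in advance: which charts, from what period, how many, what counts as still in place, and what analysis. The visible plan has none of these. If they are settled after the new-stent results are known, the choice can drive the answer.

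Comparability is also uncertain. Section C describes varied current practice: "Some inpatient procedures require stays in hospital with a tractioned vaginal stent for up to 5 days", then intermittent wear, and intermittent wear after outpatient procedures. Under F2, by contrast, "Patients will continue to wear the vaginal stent for two weeks without removal". A stent worn intermittently and one left in place continuously may not be retained in the same sense at 2 weeks.

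Second, the one retention test that G2 does specify for patients cannot stand in for the missing comparison, and it is a poor test of success in its own right. Zero retention is not a benchmark of interest, since a single retained stent already rules it out. A significant result could be reported as showing that the stent works when most stents had come out.

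**Working it through.** **1. Headcount in G1.** 20 healthy volunteers + 20 patients = 40, the stated total. G1 gives no power, effect size or comparator rate, so there is no sample-size calculation to reproduce.

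**2. The test against zero.** With k of n stents retained, the mean is k/n and its standard error is √[(k/n)(1 − k/n)/(n − 1)]. Hence t = √[k(n − 1)/(n − k)] on n − 1 degrees of freedom.

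| Retained | t | Two-sided P | One-sided P | Exact 95% CI |
|---|---|---|---|---|
| 3/20 | √(3×19/17) = 1.831 | 0.083 | 0.041 | |
| 4/20 | √(4×19/16) = 2.179 | 0.042 | 0.021 | 5.7% to 43.7% |
| 3/10 | √(3×9/7) = 1.964 | 0.081 | 0.041 | |
| 4/10 | √(4×9/6) = 2.449 | 0.037 | 0.018 | 12.2% to 73.8% |

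In all 20 patients, two-sided significance needs 4 retained stents, so 16 of 20 may be lost. One-sided, 3 of 20 is enough. With k = n the denominator n − k is zero: the best possible result has no test statistic.

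**3. How easily the test is met.** If true retention were 20% or 30% in both groups (assumed), the probability of at least 4 of 20 retained is 59% or 89% (binomial).

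**4. What 10 patients can estimate.** Exact (Clopper-Pearson) 95% intervals are:
- 8/10: 44.4% to 97.5%
- 9/10: 55.5% to 99.7%
- 10/10: lower limit 69.2%

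**5. What a specified chart comparison could show.** The documents give neither a handmade-stent rate nor a chart count, so every input here except the 10 patients is an assumption. The table gives two-sided Fisher exact power at 0.05 (new stent better), with 10 post-surgical patients and 50 charts:

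| New-stent retention | Historical 40% | Historical 50% | Historical 60% |
|---|---|---|---|
| 90% | 87% | 67% | 41% |
| 80% | 61% | 36% | 16% |
| 70% | 35% | 16% | 6% |

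Power therefore runs from 6% to 87% over this range. The study might or might not be able to detect a difference, and the documents do not allow one to say which.

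**The case against.** The strongest reply is that Aim 3b is not empty. It names the comparator, source, endpoint, time and population, and G1 describes a feasibility study meant to guide device refinement. Section D also covers a wider development project, including engineering and regulatory testing that F2 and G2 would not be expected to carry. The grant may contain the missing detail.

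Much of this stands, and it rules out three stronger readings that a reader might infer.

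- **That the study must end with no result on Aim 3b.** The aim gives enough for someone to attempt a comparison. The defect is that it would be unplanned and under-specified.
- **That F1 contradicts Aim 3b.** Saying that no control cohort is recruited does not exclude a retrospective control taken from records.
- **That the figure of 40 proves no charts are intended.** Physicians are called participants and are also outside the 40, so charts might be omitted in the same way. The headcount supports the point but does not settle it.

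It is also not established that the 10 post-surgical patients match the aim's neovaginal-surgery population. F1 admits adolescents with septa or atresia, or after radiation.

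What the reply does not answer is that G1 and G2 ask directly for numbers and comparisons, answer without this one, and do not refer to the grant. Feasibility status argues for estimating retention, not for promising superiority. The objection to the zero null does not depend on Aim 3b at all.

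**Conclusion.** The concern holds in two parts.

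The visible plan does not carry out the superiority comparison in Aim 3b, so any such comparison would be made without pre-stated charts, definitions or analysis. This part is subject to what the unavailable grant attachment contains.

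The main patient test is wrong for showing success. It can be significant with 80% of stents lost (two-sided), or 85% (one-sided, 17 of 20), and it cannot be computed if none is lost. This part rests only on G2's own wording and the stated group sizes. The 59% and 89% figures and the power table rest on assumed rates, and the table also on an assumed 50 charts. Neither part of the conclusion depends on them.

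**What to change.** 1. **G2.** Replace the one-sample t-test and its zero null with: *The main analysis estimates the proportion of stents retained at 2 weeks, with a two-sided exact (Clopper-Pearson) 95% CI, in the post-surgical and post-radiation groups separately and overall.*

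2. **Section D.** Delete both sentences of Aim 3b, or restate it as an exploratory description without the words demonstrate and superior. Aim 3a already covers two-week retention, so little is lost. Keep a comparison only if comparable charts exist, with the same wear instruction and the same definition of retained. In that case:
   - state the selection rule, period and number of charts in F2 and G1;
   - check the answer in J1 that no part of the research needs a waiver of consent, since charts of past patients may bear on it;
   - add to G2 a difference in proportions with a 95% CI, labelled non-randomised and exploratory.

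3. **F2, Phase 3.** Reconcile the post-surgical count of 20 with the 10 in Aim 3a and F1. The total of 40 fits 10. This number sets the precision of the estimate.

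**Cost.** Without the chart comparison, the change is a few sentences and one number, with no new patients or data. The price is that this study makes no superiority claim. The chart option needs a chart review and an amendment, and its power is unknown.
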